Eligible subject	Eligible subjects are subjects meeting the inclusion/exclusion criteria.
Enrolled subject	Enrolled subjects are eligible subjects who freely signed informed consent form and enrolled in the study.
Full Analysis Set	The Full Analysis Set (FAS) will comprise all subjects who provide informed consent and who are included in the study; ie, who undergo study procedures after Screening. Screening failures will not be included in the FAS. However, the number of Screening failures will be summarized in the disposition tables and all Screening failures will be listed.
Safety Population	The Safety Population will comprise all subjects in the Full Analysis Set who received at least 1 dose or a partial dose of IgPro20 in the study.
Treatment-emergent adverse event	Treatment-emergent adverse events are adverse events occurring after the start of the first IgPro20 infusion in the study and up to the End of Study visit.
Pump-Assisted Volume Cohort	Subjects testing volumes per injection site of 25 mL up to 50 mL.
Pump-Assisted Flow Rate Cohort	Subjects testing flow rates per injection site of 25 mL/hour up to 100 mL/hour.
Manual Push Flow Rate Cohort	Subjects testing flow rates per injection site of 25 to 30 mL/hour up to 120 mL/hour (equivalent of approximately 0.5 mL/minute up to 2 mL/minute)

1. Introduction

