8.4.1 Screening

All subjects, or the subjects' parent(s) or legally acceptable representative(s), must provide written informed consent before any study-specific assessments or procedures are performed. Written informed consent is not required for assessments or procedures performed according to standard of care (eg, for diagnosis or treatment); results from such assessments may be used in the determination of study eligibility.

A Screening examination should be performed between Day -35 and -7. The following procedures will be conducted and documented at the Screening visit:

- Obtain written informed consent.
- Review inclusion/exclusion criteria.
- Record information regarding medical history and demographics.
- Collect blood sample for beta-human chorionic gonadotropin for females of child-bearing potential.
- Perform a physical examination.
- Measure vital signs:
 - Systolic blood pressure, diastolic blood pressure, respiratory rate, pulse rate, and body temperature
 - Body weight
 - Height
- Collect blood samples for laboratory safety evaluation (biochemistry and hematology).
- Start recording AEs and use of concomitant therapies.

Subjects who complete all of these assessments and who fulfil the eligibility criteria (ie, eligible subjects) will be enrolled into the study. If the subject is not eligible for the study, the primary reason for screen failure must be entered in the eCRF.

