9.1 Definitions

9.1.1 Adverse Event

As per the ICH guidelines, an AE is any untoward medical occurrence in a patient or clinical investigation subject administered a pharmaceutical product and which does not necessarily have a causal relationship with this treatment. An AE can, therefore, be any unfavorable and unintended sign (including an abnormal, clinically significant laboratory finding), symptom, or disease temporally associated with the use of a medicinal (investigational) product, whether or not considered related to the medicinal (investigational) product.

The period of observation for AEs extends from the time the subject gives informed consent until the End of Study (see [Section 9.4](#) for further details).

Adverse events may include:

- Exacerbation (ie, an increase in the frequency or severity) of a pre-existing condition. Illness present before study entry should be recorded in the medical history section of the eCRF and only be reported as an AE if there is an increase in the frequency or severity of the condition during the study.
- A clinical event occurring after consent but before IgPro20 administration.
- Intercurrent illnesses with an onset after administration of IgPro20.

Adverse events do not include:

- Events identified at Screening that meet exclusion criteria.
- Medical or surgical procedures (the condition that leads to the procedure is the AE).
- Situations where an untoward medical occurrence has not taken place. For example:
 - Planned hospitalizations due to pre-existing conditions, which have not worsened.
 - Hospitalizations that occur for procedures not due to an AE (eg, cosmetic surgery).
 - Hospitalizations for a diagnostic procedure where the hospital stay is less than 24 h in duration or for normal management procedures (eg, chemotherapy).
- Overdose of IgPro20 or any concomitant therapy that does not result in any adverse signs or symptoms.

For laboratory safety parameters, any instances of absolute values being outside the reference range or changes at any visit after study start that are considered by the investigator as clinically significant must be recorded in the eCRF as AEs. In addition, at the investigator's discretion, any changes or trends over time in laboratory parameters can be recorded in the eCRF as AEs if such changes or trends are considered to be clinically relevant, even if the absolute values are within the reference range.

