3	12	7																				
4	16	10																				
5	20	12																				
6	24	15																				
7	28	17																				

Item	Definition
Success Criterion	Percentage responder for infusion parameter $p$ in cohort $c$ $R_{c,p}(\%) = \frac{100 * (\text{Number of responder for } p \text{ in cohort } c)}{\text{Number of subjects in the SAF for cohort } c}$ with the success criterion for any $R_{c,p}$ being fulfilled if $R_{c,p} \geq 33\%$ .
Start Date of Non-Response	Date of the next infusion after a subject was classified as non-responder.
Terms	
AE Rate per Infusion	Number of Adverse Events for a Particular PT / Number of Infusions Within Cohort
Baseline	Most recent non-missing value prior to or on the first study treatment dose date
Body Mass Index (kg/m  )	Body weight (kg) / Height (m) 
Compliance per Infusion (%)	(Actual amount per infusion/prescribed or planned amount per infusion)*100, where amount is dose (mg/kg) or volume (mL)
Duration of Event	End date of the event – start date of the event + 1
Elapsed Time Until Event	Event date – reference date
Local TEAEs	TEAEs identified by MedDRA high level terms “administration site reactions NEC”, “infusion site reactions”, and “injection site reactions”
Tolerability of an Infusion Parameter Within Cohort	Number of infusions without severe local reactions within cohort / number of infusions within cohort (irrespective of their validity); an infusion without severe local reactions is defined as no occurrence of a severe local reaction from the start date and time of an infusion until the start date and time of the next infusion or study end if this was the last infusion.
Treatment-Emergent	Event which started on or after the date (and time) of first administration of study treatment

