### 11.4 AEs

AEs starting on or after the date (and time if available) of the first administration of study treatment will be considered treatment-emergent AEs (TEAEs). This is the formal definition of a TEAE. It should be kept in mind that all subjects have been on a stable Hizentra® dose prior to study start.

When the AE start date is missing or partially missing, AEs will be assumed to be treatment-emergent, unless there is clear evidence (through comparison of partial dates) to suggest that the AE started prior to the first dose of study treatment. For the assignment of AEs within 72 hours after administration of treatment (temporally associated AEs), only AEs

with complete start dates will be considered. The start time will also be considered if available. AEs which start during infusion or within 72 hours after the end of an infusion will be considered temporally associated AEs.

Only TEAEs occurring until EOS visit will be included in the summary tables. All AEs will be listed.

For non-responder subjects at a certain infusion parameter level, AEs reported at the individually tolerable infusion parameter level after the non-response in the subject, i.e., AEs starting at or after the next infusion following the infusion leading to non-response, will be listed and flagged. These AEs will be analyzed separately from the AEs reported prior to that time.

AEs will be coded using the MedDRA version 20.0 or higher. AEs will be primarily classified by MedDRA PT. Analyses will be performed by SOC and PT. Aggregated incidences at SOC level and Any TEAE will also be provided.

Summaries of TEAEs will count the number of subjects, that is, subjects with multiple occurrences of the same PT will be counted once. Summaries of TEAEs will also include the number of events for each PT. Summaries will be presented for each infusion parameter and total within cohort. TEAEs will be assigned to the infusion parameter level under which they occurred. In the Total column within cohort, each subject will only be counted once with all events experienced.

AE rates per infusion will be calculated within cohort in the following way for each infusion parameter level:

- $$\text{AE Rate per Infusion} = \frac{\text{Number of Events for a Particular PT}}{\text{Number of Infusions}}$$

where number of infusions will be the sum of all infusions that subjects received within infusion parameter level irrespective of their validity as defined in Section 11.1.

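### The SAP defines a treatment-emergent AE by start date with no worsening clause, so an event open at Day 1 that worsens on study may be missing from the AE tables

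*SAP*

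**What the plan says.** Two places in the SAP define treatment emergence, and both use the start date. Section 2.2 has "Event which started on or after the date (and time) of first administration of study treatment". Section 11.4 has "AEs starting on or after the date (and time if available) of the first administration of study treatment will be considered treatment-emergent AEs (TEAEs" and calls this the formal definition, noting that subjects were already on stable Hizentra. Section 11.4 then restricts what is tabulated: "Only TEAEs occurring until EOS visit will be included in the summary tables. All AEs will be listed". Events that are not treatment-emergent go to their own listing.

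The protocol's Definition of Terms describes TEAEs as "adverse events occurring after the start of the first IgPro20 infusion in the study and up to the End of Study visit". It has no worsening clause either. Protocol 9.1.1, however, includes this among the things that may be an AE: "Exacerbation (ie, an increase in the frequency or severity) of a pre-existing condition".

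Collection begins early. At the Screening visit (Day -35 to Day -7) sites are to "Start recording AEs and use of concomitant therapies", and Protocol 9.4 starts the observation period at consent. Inclusion criteria 5a, 5c and 5d require at least one month of IgPro20 infusions at the entry level before Day 1.

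SAP Section 5 declares one departure from the protocol, on missing severity. It says nothing about treatment emergence.

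**The concern.** A start-date definition does little harm when subjects are untreated before the first dose. Here they are not. They already infuse the same product, and AEs are already being recorded, so an infusion-related event can be open when the first study infusion is given. If that event becomes more severe or more frequent on study and the site updates the existing record, its start date remains before Day 1. It is then not a TEAE, and the worsening appears only in a listing.

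What is at stake is the set of secondary endpoints in Protocol 2.2.2: the rate of all AEs, and the rate and severity of local reactions, per subject and per infusion, by infusion level. An omission of this kind can only lower the counts or severities shown. The same clinical course could be tabulated or not according to how the site chose to record it.

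**Working it through.** No figure in the plan measures this point. The one design figure, a 94% chance of an observed response rate of at least 33%, concerns responders. It reproduces as P(X ≥ 5) for X ~ Binomial(15, 0.5) = 1 − 1941/32768 = 0.941, and nothing here alters it. The check is therefore of the rules and the calendar.

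**1. Path of a worsening through the rules.** Take an AE opened after consent and before the first study infusion.

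| How the site records the worsening | Start date | TEAE under SAP 2.2 and 11.4? | In the TEAE tables? |
|---|---|---|---|
| New record dated at the worsening | After first infusion | Yes | Yes |
| Severity updated on the original record | Before first infusion | No | No, listing only |

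Neither document chooses between the two rows. Protocol 9.1.1 can be read as supporting the first. Protocol 9.5.1 (follow the course of an AE to resolution or stabilization) and 9.9 (an ongoing AE that becomes serious after study completion is sent as follow-up) lean towards the second, although that part of 9.9 concerns the period after the study.

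**2. How long the event must stay open.** SAP 8.2.2 has no Day 0, so the days from a start on Day −a to Day b are a + b − 1. From consent to Day 1 this gives 35 + 1 − 1 = 35 days at most and 7 + 1 − 1 = 7 days at least. For worsening at each level, by start day:

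| Level | First day | Start Day −1 | Start Day −7 | Start Day −35 |
|---|---|---|---|---|
| Entry level | Day 1 | 1 day | 7 days | 35 days |
| Second level | Day 29 ± 1 | 29 days (28 with the window) | 35 days | 63 days |
| Top level, volume and manual push | Day 57 ± 1 | 57 days | 63 days | 91 days |
| Top level, pump flow rate | Day 85 ± 1 | 85 days | 91 days | 119 days |

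At the entry level the event need only be open on Day 1. At any higher level it must be open for about 28 days or more. The SAP's longest duration category is more than 3 days.

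**3. What one omitted event is worth.** With 15 subjects in a cohort, one subject is 1/15 = 6.7 percentage points in a by-level incidence. That applies only if the subject has no other event with the same preferred term at that level, since subjects count once per term. For the rate per infusion at the entry level, assuming all 15 subjects complete it, a pump cohort gives 15 × 4 = 60 infusions, so one event is 1/60 = 0.017. Manual push gives 15 × 8 = 120 to 15 × 28 = 420 infusions, so one event is 0.008 to 0.002.

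**4. How many subjects are exposed.** The documents give no prevalence. If 5% to 20% of subjects had an event open at Day 1 (an assumption), that is 15 × 0.05 = 0.75 to 15 × 0.20 = 3 per cohort. This is a ceiling on subjects at risk at the entry level, not an estimate of omissions: the event must also worsen and be kept on its old record. It does not carry over to the higher levels, where the event must still be open from about Day 29.

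**5. Tolerability.** SAP 2.2 and 11.4 count any severe local reaction between the start of one infusion and the next, without saying that it must be a TEAE. The table nevertheless stands in the list of TEAE summaries, so its scope is unclear. A worsening that stops at moderate would not be counted there in either case.

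**The case against.** The strongest reply is that Protocol 9.1.1 already makes a worsening an AE in its own right. Entered that way, it starts after the first infusion and is a TEAE. The rule need not be confined to illness before consent: the laboratory exceptions in the same section treat a value abnormal at Screening as something that can become an exacerbation. The recording rule may also sit in eCRF instructions or dataset specifications outside these documents. This stands far enough that one can say only that such a worsening may be omitted. A reader might infer that it enters no AE summary table; the documents do not establish that.

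The timing objection also stands. A new reaction after any study infusion has a post-dose start and is counted, so the higher levels are affected only through an event open for about four weeks or longer. The partial answer is that the entry levels are themselves reported levels, that the definition governs systemic events too, and that nothing requires a separate record for each infusion, so a recurring reaction could be held as one long record.

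A reader might also infer that the SAP narrowed the protocol's definition without declaring it, because the protocol says *occurring* and the SAP says *starting*. The protocol definition has no worsening clause either, *occurring* can mean onset, and SAP 11.4 uses both words. An undeclared change is not shown.

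**Conclusion.** The gap is real but minor. The SAP's definition has no worsening clause, and the documents leave open how a pre-dose AE that worsens is recorded, so some worsening may be missing from the descriptive AE rate and severity tables. The effect falls mainly on the entry level. Its size is unknown and probably small; the 5% to 20% range above is an assumption that bounds only the subjects at risk.

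A reader might infer that this biases the label recommendation. It does not. Protocol 11.3.5 and SAP 11.1 set the recommended level by a responder rate of at least 33%, built from valid infusions. Validity rests on volume or rate, dose, interruption and prohibited medication. The only AE condition, in the SAP's modified definition for the pump cohorts, concerns related events that begin during an interrupted or stopped infusion. AE rates play no part. Nor do the documents support the idea that the higher levels are flattered relative to the entry level, since any omission falls mostly on the entry level itself.

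**What to change.** - In SAP 2.2 and 11.4, define a TEAE as an AE that starts on or after the first study infusion, or that started earlier and increases in severity or frequency, or becomes serious, on or after it.
- State that the worsening is recorded as a new AE, dated at the worsening and assigned to the infusion level in use on that date. Give sites the matching eCRF instruction.
- State whether the tolerability table counts all severe local reactions or only TEAEs.

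The cost is a wording change (by SAP amendment, as SAP Section 5 requires once the plan is final), one eCRF instruction and minor programming. AE counts may rise slightly. No sample size or design figure changes.

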An infusion parameter will be considered successfully achieved if at least one third of the subjects in the corresponding cohort (5 of 15) are responders at that infusion parameter level, as defined above. The highest achieved infusion parameter level will be used for the label change. The rationale for this is based on medical experience (personal communications with several key opinion leaders and limited clinical research experience). A response rate for reaching the top infusion parameter for each endpoint of 50% is assumed. Using a binomial distribution with 15 evaluable subjects, there will be a 94% probability that the observed response rate for a single endpoint in the study is $\geq 33\%$.

Excluding the differences in infusion parameters/administration, all 3 cohorts have a similar overall study design (including AE collection). A schematic overview of the study is presented in [Figure 1](#).

Figure 1. Study Overview

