Manual Push Flow Rate Cohort	
 
• The actual infusion duration is no more than 1 minute or 10% (whichever is longer) longer than the calculated infusion duration based on the desired flow rate (i.e., 30 mL/h [0.5 mL/min], 60 mL/h [1 mL/min], or 120 mL/h [2 mL/min]) and the actual volume infused and
 
• No prohibited concomitant medication and
 
 
The actual infusion volume is at least 95% of the planned infusion volume for that infusion day over all infusion sites.
																					
Definition of Responder per Infusion Parameter Level																						
Pump-Assisted Volume Cohort	≥ 3 valid infusions in any order (out of 4 infusions)																					
Pump-Assisted Flow Rate Cohort	≥ 3 valid infusions in any order (out of 4 infusions)																					
Manual Push Flow Rate Cohort	
≥ k valid infusions in any order during the 4 weeks planned for that infusion parameter level, with k being
 
  
 Manual push infusions per week	Total number of infusions scheduled for parameter set	Minimum number of valid infusions (k)	
   
 2	8	5	
 
 3	12	7	
 
 4	16	10	
 
 5	20	12	
 
 6	24	15	
 
 7	28	17	
  
	Manual push infusions per week	Total number of infusions scheduled for parameter set	Minimum number of valid infusions (k)	2	8	5	3	12	7	4	16	10	5	20	12	6	24	15	7	28	17
Manual push infusions per week	Total number of infusions scheduled for parameter set	Minimum number of valid infusions (k)																				
2	8	5																				

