#### **4.5 Determination of the Sample Size**

The sample size for this study is not determined based on hypothesis testing considerations. A minimum of 45 evaluable (15 per cohort) subjects will be needed. This is based on an assumed response rate for reaching the top infusion parameter for each endpoint of 50% (i.e., 100 mL/h for the Pump-Assisted Flow Rate Cohort, 50 mL per injection site for the Pump-Assisted Volume Cohort, and 2 mL/min for Manual Push Flow Rate Cohort). Using a binomial distribution with 15 evaluable subjects, there will be a 94% probability that the observed response rate for a single endpoint in the study is  $\geq 33\%$ .

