#### 8.1.2 Imputation of Partial Dates

A worst-case approach will be used to assign AE flags or concomitant medication flags if start dates of AEs or concomitant medications are missing or partially missing. Details are given in the respective sections. Study day, durations, or other time variables based on dates

cannot be calculated for partially missing start dates and thus will be missing. Except for the calculation of the duration of an AE for which the following approach will be used: For the calculation of the duration of an AE, missing end dates will not be imputed for AEs which are ongoing. For ongoing AEs the end date and thus the duration will not be available by definition. If the outcome of the AE indicates that the AE is resolved but the end date is still completely missing, the data entry date for this information will be used as AE end date. If only the end day is unavailable, the last day of the month or the subject's study end date whatever occurs first will be imputed as AE end date for the calculation of the AE duration. This approach will be followed in order to avoid underestimation of durations of AEs.

Missing infusion end date and time will be imputed by adding the infusion duration to the infusion start date and time.

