**Table 3: Responder requirements in Manual Push Flow Rate Cohort**

Manual push infusions per week	Total number of infusions scheduled for parameter set	Minimum number of valid infusions ( $k$ )
2	8	5
3	12	7
4	16	10
5	20	12
6	24	15
7	28	17

Rationale for number of valid infusions to qualify a responder in the Manual Push Flow Rate Cohort: The probability for a subject to be a responder for a certain infusion parameter is assumed to be 50% irrespective of the value of the infusion parameter itself, i.e. identical to the assumed response rate in Clinical Study Protocol Section 11.1. This assumption is based on the expectation that there will be no infusion-related reasons for a subject to interrupt the infusion or change the infusion parameters. To achieve  $\geq 3$  out of 4 valid infusions the probability for a single infusion to be valid has to be  $\geq 61\%$  for Pump-Assisted Cohorts. Using this 61% success probability for a single infusion in the Manual Push Flow Rate Cohort the minimum number of successes (k) in Table 3 corresponds to a probability for a subject to be a responder of at least 50%.

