and will be presented by infusion parameter and cohort. The number of infusions irrespective of their validity as defined in Section 11.1 will be used as denominator for the assessment of tolerability. The total number of infusions within infusion parameter level and within cohort will be considered as denominator for the tolerability within infusion parameter level and within cohort, respectively. An infusion without severe local reactions is defined as no occurrence of a severe local reaction from the start date and time of an infusion until the start date and time of the next infusion or study end if this was the last infusion.

Local TEAEs will be identified by the MedDRA high level terms “administration site reactions NEC”, “infusion site reactions”, and “injection site reactions”. The MedDRA high level terms will be reviewed prior to database lock and the list of terms to be included into Local TEAEs will be updated. Local TEAEs will be included in all tables by using a virtual SOC called “Local Adverse Events”. In addition, the local TEAEs will also be presented by their MedDRA SOC “General disorders and administration site conditions”.

TEAEs will be sorted in descending order of total incidence by SOC and PT.

The summary will report for the Any TEAE row, each SOC, and each PT, the number of subjects with at least one TEAE, counted for the maximum reported severity in the table by severity. Local TEAEs will be reported only once in the Any row.

A listing of MedDRA SOC, PT, and verbatim text will be provided.

All AEs will be listed. TEAEs will be listed for the SAF. Other AE listings will use all available data. The listings will include the variables as specified in Section 7 and in addition MedDRA SOC, PT, and the verbatim, AE start and end date and time if available, duration of AE in days, severity, serious (yes or no), relationship to treatment (yes or no), outcome, action taken, and AE flags (TEAE, SAE, temporal relationship within 72h [AE72h]). Additionally, a listing of subject IDs for each individual PT will be produced.

The following listings will be provided:

- Non-TEAEs – all available data;
- TEAEs – SAF;
- Deaths – all available data;
- SAEs – all available data;
- AEs leading to study discontinuation – all available data;
- Local TEAEs – SAF;
- MedDRA SOC and PT with all AE verbatim – all available data;
- Subject IDs for each PT – all available data.

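### SAP 11.4 reverses the worst-case rule of SAP 8.1.2 for the 72-hour AE flag, and the SAP text has no rule for placing incompletely dated AEs in a level or a tolerability window

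*SAP*

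**What the plan says.** SAP 8.1.2 sets the general principle: "A worst-case approach will be used to assign AE flags or concomitant medication flags if start dates of AEs" or of concomitant medications are missing or partly missing. It leaves details to the individual sections. It imputes AE end dates for calculating duration, but not start dates; other time variables that need a partial start date stay missing.

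SAP 11.4 lists three AE flags: treatment-emergent, serious, and within 72 hours of treatment (AE72h). Two have an explicit rule for incomplete start dates:

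- **Treatment-emergent:** the AE is assumed to be treatment-emergent unless the partial date clearly shows otherwise.
- **AE72h:** only AEs "with complete start dates will be considered".

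Two further placements depend on timing:

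- **Level:** each TEAE goes to the infusion parameter level under which it occurred (SAP 7 and 11.4).
- **Tolerability:** an infusion counts as tolerated if there was "no occurrence of a severe local reaction from the start date and time of an infusion" until the next infusion starts, or until study end for the last one. The denominator is all infusions, valid or not.

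Neither placement comes with a rule for an incomplete AE start date.

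**The concern.** The same missing information is handled conservatively for one flag and favourably for another, under a section that announces a conservative approach for AE flags in general. An AE with only a month and year is treatment-emergent by assumption but is kept out of the 72-hour table.

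The silence on windows matters more for tolerability. That definition looks for a severe local reaction between two infusion start times. If a reaction cannot be located between any two, no infusion fails, yet all infusions remain in the denominator. An error of this kind can only raise tolerability, and an event left out of a level can only lower that level's rate.

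Tolerability by level and local reaction rate by level are both secondary endpoints. Few severe reactions are expected: Protocol 1.4 reports that 99% of AEs in the three pivotal studies were mild or moderate. A single event could therefore be the difference between 100% and something less at one level.

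**Working it through.** **1. The plan's own figure.** SAP 4.5 states: "A minimum of 45 evaluable (15 per cohort) subjects will be needed". It takes an "assumed response rate for reaching the top infusion parameter for each endpoint of 50"%, and Protocol 3.1 sets success at "at least one third of the subjects in the corresponding cohort (5 of 15) are responders". Then P(X ≥ 5 | n = 15, p = 0.5) = 1 − (1 + 15 + 105 + 455 + 1365)/2^15 = 1 − 1941/32768 = 0.941. This reproduces the stated 94%. The point does not depend on this figure; it only confirms 15 subjects per cohort as the design basis.

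**2. Infusions per level.**

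- Pump cohorts: 4 per subject (SAP 2.2: "≥ 3 valid infusions in any order (out of 4 infusions"). With 15 subjects, 15 × 4 = 60.
- Manual push: 8 to 28 per subject (SAP Table 3, column "Total number of infusions scheduled for parameter set"). With 15 subjects, 15 × 8 = 120 to 15 × 28 = 420.
- Higher pump levels may have fewer subjects. The documents do not say how many will enter, so 8 and 5 subjects are assumed: 32 and 20 infusions.

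**3. Effect of one unplaced severe local reaction.** If it is charged to one infusion, tolerability is (N − 1)/N. If it is left unplaced, and there is no other severe reaction, tolerability is N/N. The overstatement is 1/N.

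| Level | N | Charged | Unplaced | Overstatement (points) |
|---|---|---|---|---|
| Pump, 15 subjects | 60 | 98.3% | 100% | 1.7 |
| Pump, 8 subjects (assumed) | 32 | 96.9% | 100% | 3.1 |
| Pump, 5 subjects (assumed) | 20 | 95.0% | 100% | 5.0 |
| Manual push, 2 per week, 15 subjects | 120 | 99.2% | 100% | 0.8 |
| Manual push, 7 per week, 15 subjects | 420 | 99.8% | 100% | 0.2 |

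**4. How often a month-only date can still place the AE.** All 365 treatment start days in one calendar year were enumerated, with 28-day levels and 7-day infusion windows. Each on-treatment day was treated as an equally likely AE day. The count is of days whose calendar month, cut to on-treatment days, lies within a single level or window.

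| Schedule | Single level fixed | Single weekly window fixed |
|---|---|---|
| 84 days | 32% | 2.2% |
| 112 days | 24% | 1.6% |

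A month-only date thus identifies the level in about a quarter to a third of cases, but the window almost never. Manual push windows are shorter than a week, so they would be harder still to identify.

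**The case against.** The strongest replies are these.

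- **The sections may set the detail.** SAP 8.1.2 defers to them and says time variables cannot be computed from partial start dates, so the 72-hour restriction could be the promised detail. This explains how the text arose. It does not remove the conflict: AE72h is listed as an AE flag, and a detail that gives the most favourable result is not a worst case.
- **The missing rule may exist elsewhere.** SAP 8.2 refers to separate analysis dataset specifications for full derivation details. Those are not available here, so the gap is shown only for the SAP text. This stands.
- **Incomplete dates may be rare.** Subjects record AEs in an eDiary, staff review it at office visits every four weeks, and queries are raised. This stands as a limit on likelihood.

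A reader might infer more than the documents support:

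- *That these AEs are barred from every level and window.* The complete-date restriction is written only for the 72-hour group. Elsewhere the SAP is silent, and a partial date sometimes fixes the level.
- *That the combined related-or-within-72-hours table loses them all.* An AE enters that table on causality alone, and SAP 11.4 treats missing causality as related. Only AEs judged not related drop out.
- *That the event disappears.* It stays in the cohort Total column of the AE tables and in the listings.
- *That half the cohort enters the top level.* The 50% is an assumed response rate there; entrants include non-responders.
- *That the primary endpoint or label criterion shifts.* The per-protocol valid-infusion definition uses no AE date. Only the modified definition could be touched, since it asks whether a related AE began during an interrupted or stopped infusion.

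**Conclusion.** The point holds in two parts. First, SAP 11.4 contradicts the worst-case principle of SAP 8.1.2 for the 72-hour flag, by a stated rule and in the favourable direction. Second, the SAP text gives no rule for placing an incompletely dated AE in a level or a tolerability window, so a severe local reaction can leave tolerability unchanged, both by level and for the cohort as a whole.

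The sizes in the table apply per event. They assume that a severe local reaction with an incomplete date occurs, that it would count against exactly one infusion, and, for the smaller pump levels, that 8 or 5 subjects contribute four infusions each. How often this would happen cannot be judged from the documents. The analysis is descriptive, and the per-protocol responder rate with its 33% criterion is untouched. This is a worthwhile clarification of secondary safety outputs, not a threat to the main conclusion.

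**What to change.** In SAP 11.4:

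1. Flag a TEAE with a missing or partial start date as temporally associated unless the partial date rules it out.
2. For a severe local reaction that cannot be placed in a window, count one infusion as not tolerated at the highest level compatible with the partial date, and also in the cohort total.
3. Footnote the affected tables with the number of AEs assigned this way.

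The cost is a few SAP sentences and some programming. The downside is that reactions at the higher level may be slightly overstated, and those at a lower level understated; a fully missing date would default to the highest level the subject used. The footnote lets a reader see how much of any difference between levels rests on the rule.
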